**Figure 2.**

[figure not shown]
Experimental design: upper portion gives the design of the entire experiment. Lower part depicts an example of each run type (order of conditions balanced within and between subjects). Shock blocks can be concurrent with tasks described below. When subjects are participating in a no-shock run, the tasks will replace the shock blocks as indicated above. Subjects do not engage in any specific task during resting state runs.

Each condition will have an identical duration of two minutes, and be identical with respect to number of stimulus cues presented. Virtual reality environments (e.g., restaurant scene, airport scene, pool scene) may be used as cues to allow for a richer and clearer differentiation of predictable, unpredictable and neutral conditions. The predictable condition will be defined as the context in which shocks can only occur during an explicit stimulus cue. Subjects will be informed that they will not receive a shock during any other time during this condition. The stimulus cue will appear for approximately 1-8 seconds. The unpredictable condition will be defined as the context in which shocks can be delivered without warning at any time. Furthermore, shocks will be administered to reinforce these instructions with the same number during predictable and unpredictable conditions. Occasional reinforcement is necessary to prevent the instructions from losing credibility. Finally, the neutral condition will be defined as the context in which participants are completely safe from receiving shocks.

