The determination of the amount of money disbursed will be as follows. First, to provide a more real-life situation and enhance motivation to gamble and engagement in the task, we will provide an initial endowment of \$20.00 that can be lost during the task. This endowment will make the potential losses real. At the end of the task, we will randomly select three gambles from the total number of gambles (n=512) presented to the participants. To do so, we will ask participants to randomly pick 3 numbers between "001" and "512". We will then identify the gambles corresponding to these 3 gambles and add the gains and losses from these 3 gambles. Participants can earn up to \$50.00 or lose up to \$20.00 (entire endowment). We have already used this strategy in previous protocols (e.g., 01-M-0192).

*Motivation/ "Monetary Incentive Delay" Task (Healthy N=150; Patients N=30):*

Participants will perform one of two versions of the "Monetary Incentive Delay" task. During the first version of the task (N = 80 HVs on the 3T scanner and N= 30 HVs on 7T scanner), we will examine the effect of threat of shock on goal-driven/ motivational stimuli. We will use a paradigm during which subjects make speeded responses to a central target under conditions of potential monetary gain, loss or neutrality during threat of shock and during safety. During each trial of the task, participants will first see one of three shapes, either a circle, a square, or a triangle, then wait for a variable time interval, and finally respond to a white box

with a button press. Trials beginning with a circle indicate that the subject will win money if s/he presses the button fast enough once the white box appears; trials beginning with a square indicate that the subject will lose money if s/he does not press the button fast enough once the white box appears; trials beginning with the outline of a triangle indicate that the subject will neither lose nor win money, independent of task performance. Participants will perform this version of the Monetary Incentive Delay task within the MRI scanner.

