During the second version of the task (N = 40 HVs), we will examine the impact of monetary incentives and aversive stimuli on goal-driven / motivational processing. We will use a paradigm during which subjects make speeded responses to a central target during four types of trials. Accurate responses to the central target will determine whether participants: 1) win money (gain trials), 2) avoid losing money (loss trials), 3) avoid the presentation of an aversive electrical stimulus (aversive trials). During 4) even trials, participants will never receive monetary or aversive stimuli, regardless of performance. During each trial of the task, participants will first see a cue denoting the type of trial, then wait for a variable time interval, and finally respond to a white box with a button press. Participants will perform this version of the Monetary Incentive Delay task within the MEG scanner.

During both versions of the modified Monetary Incentive Delay task, the shape at the beginning of the trial serves as a signal characterizing the trial type. Additionally, participants will receive feedback after each trial indicating whether they succeeded in responding to the target fast enough. The duration of the white box is adjusted such that each participant succeeds on approximately 66% of his or her responses. Participants will be informed that "Your performance during each trial will determine whether you win money or lose money. However, the task may become more difficult or less difficult over time. Please try your best at all times."

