For the second modified version of the *Motivation/ "Monetary Incentive Delay" Task*, we propose to collect 40 participants on the MEG scanner to assess anticipatory responses to aversive and monetary motivational stimuli. Assuming a medium effect size (Cohen's  $d_z=0.5$ ), a power of 0.8, and an alpha of 0.05, power analyses suggest that we would require a sample of 34 participants to detect a difference between conditions employing two-tailed paired T tests. Assuming five participants are lost due to head motion, we will need to collect 40 participants to detect a medium sized effect of trial type on anticipatory neural responses.

Collectively, the three research projects listed above ( $80+30+40=150$ ) will increase our accrual from 30 to 150 participants for the *Motivation/ "Monetary Incentive Delay" Task*.

For the first modified version of the *Active Avoidance of Signaled Threat Paradigm*, we propose to collect 45 healthy participants without war-zone exposure on the fMRI scanner. Assuming a medium effect size (Cohen's  $d_z=0.5$ ), a power of 0.8, and an alpha of 0.05, power analyses suggest that we would require a sample of 34 participants to detect a difference between conditions employing two-tailed paired T tests. Assuming ten participants are lost due to head motion and poor performance, we will need to collect 45 participants to detect a medium sized effect of trial type on neural responses during avoidance.

For the second modified version of the *Active Avoidance of Signaled Threat Paradigm*, we propose to collect 45 healthy participants without war-zone exposure on the MEG scanner. Assuming a medium effect size (Cohen's  $d_z=0.5$ ), a power of 0.8, and an alpha

of 0.05, power analyses suggest that we would require a sample of 34 participants to detect a difference between conditions employing two-tailed paired T tests. Assuming ten participants are lost due to head motion and poor performance, we will need to collect 45 participants to detect a medium sized effect of trial type on neural responses during avoidance.

Collectively, the two research projects listed above (45+45=90) will increase our accrual from 30 to 90 healthy participants without war-zone exposure for the *Active Avoidance of Signaled Threat Paradigm*.

*d. Accrual number*

Our ceiling is set at 1952 participants. This will account for the addition of patients (726) as well as a separate group of 1226 healthy matched (age, sex, IQ) controls.

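### In version 1 of the Monetary Incentive Delay task (3T and 7T MRI) each cue shape is tied to one trial type with no rotation described, so the trial-type contrast that sizes the 7T sample also contains the response to shape

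*Combined protocol and SAP*

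**What the plan says.** The task description in section 4.iv of the protocol (Motivation / Monetary Incentive Delay Task) gives version 1 to two MRI samples: "N = 80 HVs on the 3T scanner and N= 30 HVs on 7T scanner". Participants respond under "conditions of potential monetary gain, loss or neutrality during threat of shock and during safety". One set of cues is given:

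- gain: "Trials beginning with a circle indicate that the subject will win money if s/he presses the button fast enough"
- loss: "trials beginning with a square indicate that the subject will lose money if s/he does not press the button fast enough"
- neutral: "trials beginning with the outline of a triangle indicate that the subject will neither lose nor win money, independent of task performance"

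No alternative assignment appears, and nothing says that shapes are rotated or counterbalanced over participants. Balancing is mentioned in the caption to Figure 2, for the order of conditions in the general threat design, and in the ValSal task, for the order of blocks. Neither concerns which stimulus stands for which condition.

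Section 10.c sizes the 7T sample for a difference between trial types by a two-tailed paired t test. The 3T sample is sized differently, for a multiple regression on gender and trait anxiety.

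Version 2 is run in the MEG scanner with four trial types. Its own description mentions only an unspecified cue. A later sentence covering both versions adds that "the shape at the beginning of the trial serves as a signal characterizing the trial type", without naming shapes for version 2. Its sample is also sized on trial type: "we will need to collect 40 participants to detect a medium sized effect of trial type on anticipatory neural responses".

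**The concern.** In version 1 as written, a participant who sees a gain cue always sees a circle, and one who sees a neutral cue always sees a triangle. A gain-minus-neutral difference is therefore also a circle-minus-triangle difference. If every participant has the same mapping, this part of the contrast has the same expected value in everyone. More participants do not average it away, and no model term can separate it from incentive.

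The exposure falls on the 7T sample, because trial type is the contrast on which that sample is justified. Section 10.a also plans a voxel-wise analysis outside the regions of interest. Visual and attention areas, where a shape response is most plausible, can therefore be tested and reported. A difference found there could be read as an incentive effect when it is partly or wholly a response to the cue's appearance.

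**Working it through.** **1. The plan's own 7T figure.** Inputs from section 10.c: dz = 0.6, power 0.8, alpha 0.05, two-tailed paired t test, 24 required, five expected losses, 30 to be enrolled.

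Formula: power = P(|T| > t(0.975, n−1)), with T noncentral t on n−1 degrees of freedom and noncentrality dz × √n. At n = 24 the noncentrality is 0.6 × √24 = 2.94 and power is 0.804. This is the smallest n that reaches 0.80, so the stated 24 reproduces. Then 24 + 5 = 29 against 30 planned, and 30 − 5 = 25 evaluable, with power 0.821. The sample size is not in dispute.

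**2. What the contrast estimates.** Write a participant's gain-minus-neutral difference as incentive effect + (circle − triangle) + error. Under one mapping the mean over participants has expectation incentive effect + (circle − triangle), whatever n is.

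**3. What rotation does.** Write c, s and t for the responses to circle, square and triangle. A three-way Latin square gives:

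| Mapping | Gain | Loss | Neutral | Shape part of gain − neutral |
|---|---|---|---|---|
| A | circle | square | triangle | c − t |
| B | square | triangle | circle | s − c |
| C | triangle | circle | square | t − s |

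The last column sums to zero. The same holds for gain − loss, (c − s) + (s − t) + (t − c), and for loss − neutral, (s − t) + (t − c) + (c − s). With equal groups the expected shape contribution is zero.

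**4. Illustration of size.** The documents give no shape effect, so dz 0 to 0.3 is an assumption. Take a true incentive effect of zero, n = 25 and one two-sided test at 0.05:

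| Shape effect (dz) | Noncentrality, dz × √25 | Probability of rejection |
|---|---|---|
| 0 | 0 | 0.050 |
| 0.1 | 0.5 | 0.077 |
| 0.2 | 1.0 | 0.161 |
| 0.3 | 1.5 | 0.302 |

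The sign is unknown too. If shape opposed a true incentive effect of dz 0.6 by 0.2, with the same standard deviation, the contrast would have dz 0.6 − 0.2 = 0.4 and power 0.484 instead of 0.821.

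**5. Contrasts that escape.** Threat minus safe within gain trials compares a circle with a circle, so the shape term cancels. The same holds within loss and within neutral trials.

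**The case against.** The strongest reply is that the outcomes the plan names are not those most exposed. Version 1 is introduced as a study of how threat affects motivational processing, and threat-safe contrasts within a trial type are clean. The 7T sample targets small structures in the midbrain, not visual cortex, and nothing in the documents shows how much a shape response would enter there. The task description is short, and silence on counterbalancing does not prove that shapes were never rotated. All of this stands, and it limits the weight of the point. It does not remove it: the 7T sample is sized on trial type, and the written procedure separates trial type from shape nowhere.

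A reader might infer three stronger things that the documents do not support.

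- **That the MEG sample has the same fixed mapping.** The circle, square and triangle assignment is written for version 1 only. The sentence covering both versions fits a rotated assignment equally well. The supportable statement is that the MEG mapping is unspecified, so the rejection rates above should not be carried over to MEG.
- **That the virtual reality scenes have the same flaw.** The text says only that "Virtual reality environments (e.g., restaurant scene, airport scene, pool scene) may be used as cues". They are optional examples, and no scene is assigned to any condition.
- **That the neutral cue differs in fill.** Only the triangle is called an outline, but the same paragraph first lists the three shapes without that word, and nothing says that the circle and square are filled.

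**Conclusion.** The point holds for version 1, and it matters most for the 7T sample. If the protocol is followed as written, cue shape and incentive are confounded in every comparison of trial types. That the mapping is the same for all participants is inferred from the single assignment given and the absence of any statement of rotation.

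The size cannot be established from the documents. Under an assumed shape effect of dz 0 to 0.3 and no incentive effect, the rejection rate at 25 evaluable participants is 5% to 30% instead of 5%. That range describes a single region where such a shape effect exists. It is not an estimate for the midbrain target, and it says nothing about a corrected whole-brain map. The 3T sample uses the same cues, but its size rests on a between-subject regression. Any trial-type contrast reported from it needs the same caution.

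This is an inexpensive improvement to the design. It is not a reason to doubt the sample size or the threat-safe results.

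**What to change.** 1. **Version 1.** Rotate the shape-to-trial-type assignment across participants with the three-way Latin square above, and match the shapes for fill and luminance. At 7T, 30 participants give ten per mapping.
2. **Analysis.** Once rotated data exist, enter mapping as a between-subject factor and weight the mappings equally. With 25 evaluable participants the error degrees of freedom fall from 24 to 22.
3. **Participants already run under the single mapping.** Mapping does not vary within such a cohort, so no factor can be estimated there. State that shape and incentive cannot be separated in those data, and do not attribute trial-type differences in visual or attention areas to incentive.
4. **Version 2 (MEG).** State which cue stands for which trial type and apply a four-way rotation. Forty participants give ten per mapping.
5. **If rotation is already practised,** one sentence in section 4.iv saying so settles that part of the point.

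The cost is a change to the stimulus script, a check of the stimuli and one nuisance factor, with no change in planned enrolment. If enrolment has begun, the combined data will mix mappings, and mapping will be partly confounded with enrolment period. The report should say so.

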C) A third hypothesis is that while anticipation of unpredictable shocks will reduce GABA concentration, leading to low peak frequency of stimulus-induced gamma oscillations in the occipital cortex and increases BOLD response, the benzodiazepine alprazolam will have the opposite effect (increased GABA, leading to high peak gamma frequency and decreased BOLD signal).

D) A fourth hypothesis is that under threat of shock, prefrontal executive control regions will be less successfully engaged by patients with high anxiety or MDD than healthy controls. Further, we predict that both patient groups will recruit the cortical and subcortical limbic regions (e.g., amygdala, bed nucleus of stria terminalis (BNST), and insula) to a greater extent than healthy controls when under threat of shock. In contrast to anxiety patients, MDD patients will additionally recruit subgenual/rostral ACC in response to threat.

E) In the PTSD hippocampus investigation, we hypothesize that the hippocampus and dorsolateral prefrontal cortex (dlPFC) will play a key role in the effect of anxiety on BPS Task performance and that participants with PTSD will exhibit amplified pattern separation deficits. We also hypothesize that pattern separation deficits will be associated with PTSD symptom severity in the dentate gyrus as indicated in the high-field 7-Tesla resting state scan. Lastly, we hypothesize that the PTSD group (vs. no-PTSD) will have increased hippocampal-dependent spatial memory deficits on the Morris water maze (MWM) task.

F). We hypothesize that during the AAST paradigm, participants will exhibit enhanced neural responses to the avoidance cue during the threat-of-shock condition, within areas of the medial prefrontal cortex, amygdala, and striatum. Furthermore, we hypothesize that participants with PTSD will exhibit reduced medial prefrontal cortex responses during threat contexts, and elevated avoidance behavior. Lastly, we hypothesize that individual differences in avoidance behavior will be associated with the magnitude of task elicited neural activity within the medial prefrontal cortex, amygdala, and striatum.

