Participants will perform a modified version of the active avoidance of signaled threat paradigm (Gorka, LaBar, & Hariri, 2016), during which, they will hold down a button and view sequentially presented pairs of colored squares. The squares will differ based on the color's hue (low, medium, and high). Participants will be instructed to lift their finger when they see the medium-medium color combination (i.e. “go” trials), and to refrain from lifting their finger during all other combinations (i.e. “stop” trials). Participants will perform alternating blocks in safe and threat conditions, and each block will consist of a series of “go” and “stop” trials.

We will use independent stair-case procedures to titrate task difficulty so that all participants achieve a ~75% accuracy during go trials for each condition. During the threat condition, participants will receive an electrical shock whenever they make a mistake. Participants will be informed that “Your performance during each trial will determine whether or not you receive an electrical shock. However, the task may become more difficult or less difficult over time. Please try your best at all times.” During the safe condition, participants will never receive an electrical shock. The duration of each electrical shock will not last longer than

100 milliseconds. The frequency of delivery for electrical shocks will be based on performance, but a minimum of 10 seconds will separate each electrical shock. No participant will receive more than 10 electrical shocks in this substudy regardless of their performance. The amplitude of the electrical shock will be selected by the participant, through the shock workup protocol (see section 8, Electric shocks: work-up), to correspond to a level which the participant perceives to be tolerable, yet aversive. The shock intensity will not go above the 100 mA maximum shock intensity outlined in the protocol (see section 4iv., Electric shocks as unconditioned stimulus). These parameters have been well tolerated by participants in our previous studies.

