Healthy controls without war-zone exposure will perform the task in the MEG or MRI scanners. Healthy controls with war-zone exposure and participants with PTSD from war-zone exposure will perform the task in the MRI scanner. Differences in accuracy and reaction times between the safe and threat condition will serve as measures of active avoidance, and will be used to determine whether persons with PTSD exhibit impaired or facilitated behavioral responses to threat. Indices of neural circuit function will be used to determine whether persons with PTSD exhibit altered neural responses during active avoidance, and whether changes in neural circuit function are associated with individual differences in active avoidance behavior (i.e. accuracy and reaction time).

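### The active-avoidance task titrates go-trial accuracy to about 75% in both conditions, then uses the safe-threat accuracy difference to judge avoidance in PTSD

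*Combined protocol and SAP*

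**What the plan says.** Section 4.iv, Active Avoidance of Signaled Threat Paradigm, describes safe and threat blocks that each contain go and stop trials. On go trials participants lift a finger; on stop trials they must "refrain from lifting their finger during all other combinations". Difficulty is adaptive: "We will use independent stair-case procedures to titrate task difficulty so that all participants achieve a ~75% accuracy during go trials for each condition". No titration is stated for stop trials.

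The outcome paragraph of the same section says: "Differences in accuracy and reaction times between the safe and threat condition will serve as measures of active avoidance". These differences are to show whether persons with PTSD respond worse or better under threat. They also supply the behavioural side of the brain-behaviour analysis, described as "individual differences in active avoidance behavior (i.e. accuracy and reaction time".

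Hypothesis F in section 2 predicts elevated avoidance in PTSD and that "individual differences in avoidance behavior will be associated with the magnitude of task elicited neural activity". Sections 9 and 10 do not define the accuracy measure further. The task's sample size in section 10.c is set to "detect a medium sized effect of trial type on neural responses during avoidance", which is a separate matter.

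**The concern.** A staircase run separately in each condition makes the task harder for whoever is doing well and easier for whoever is doing badly, until go accuracy sits near the target. If threat sharpens performance, the staircase absorbs the gain: the difficulty level moves and the accuracy does not. Scoring the accuracy difference as the effect means scoring the quantity the procedure equalises.

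Two readings would suffer. A small or null PTSD-control difference in go accuracy could be reported as no impairment or facilitation. A weak brain-behaviour correlation could reflect a behavioural score with little information left in it. If go and stop trials are pooled, the titrated trials also dilute any real stop-trial difference.

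**Working it through.** **1. The plan's own figure.** Section 10.c asks for 34 analysable participants for a two-tailed paired t test with dz = 0.5, power 0.8 and alpha 0.05. Exact noncentral-t power is 0.808 at n = 34 and 0.795 at n = 33, so 34 is reproduced (34 + 10 lost = 44, against 45 stated). That figure concerns neural responses, and this point does not rest on it.

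**2. The two statements together.** If titration works, the expected go-accuracy difference is 75% − 75% = 0 in every group, and so is the PTSD-control contrast on it.

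**3. What can survive.** The plan gives no staircase rule. Assume one that becomes harder by s after a correct go trial and easier by 3s after an error. It balances where p·s = (1 − p)·3s, so p = 0.75. Over n scored trials with C correct, the level moves by s·C − 3s·(n − C), so

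C/n = 0.75 + (end level − start level)/(4·s·n).

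With a common start and all trials scored, the threat-safe accuracy difference is therefore the difference in end levels divided by 4sn. It is a shrunken trace of the staircase level. For a shift of 0.5 probit that the staircase fully tracks:

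- s = 0.2, n = 200: 0.5/160 = 0.3 points.
- s = 0.05, n = 30: 0.5/6 = 8.3 points (6.7 is the largest simulated value below; so short a staircase has not caught up).

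**4. Benchmark at fixed difficulty.** Assume probit performance, ability SD 0.5, threat shift of mean 0.5 and SD 0.3, and difficulty set at the average person's 75% point (z = 0.674). Mean accuracy is Φ(0.674/√1.25) = 0.727 in safe and Φ(1.174/√1.34) = 0.845 in threat, a difference of about 12 points. An extra shift of 0.3 in PTSD gives Φ(1.474/√1.34) = 0.899, a further 5.4 points.

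**5. Simulation.** There were 72 settings: three starts (common at the average 75% level, common and 1 z easier, calibrated per person and condition with SD 0.15); s of 0.05, 0.1 or 0.2; 30, 60, 100 or 200 go trials per condition; 0 or 20 early trials dropped. Each used 20,000 simulated participants. All settings are assumptions. Here dz is the mean difference over its SD, and r is the correlation with each person's true threat effect.

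| Measure | Difference, points | dz | r |
|---|---|---|---|
| Fixed-difficulty accuracy | about 12 | 0.91-1.31 | 0.47-0.68 |
| Go accuracy, common start, all trials | 0.3-6.7 | 0.62-1.09 | 0.37-0.66 |
| Go accuracy, common start, 20 dropped | 0.0-5.0 | 0.0-0.64 | 0.0-0.42 |
| Go accuracy, calibrated start | within 0.12 of zero | about 0 | about 0 |
| Staircase level | not applicable | 0.74-1.55 | 0.39-0.92 |

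The level had the higher dz in 70 of the 72 settings.

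A second model (logistic, step 0.15, shift 0.5 to 1.0 logit) gave 0.1 to 0.3 points after a 20-trial run-in with 60-100 scored trials, against 8 to 14 at fixed difficulty. With no run-in and 40-60 trials, 1.4 to 4.2 points remained. The formula in step 3 predicts 0.5/(4 × 0.15 × 60) = 1.39 points for one of these settings; the simulation gave 1.36.

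**6. PTSD against controls.** The setting was 30 v 30, a two-sample t test at two-sided 0.05, an extra shift of 0.3 probit, a common start unless stated, 60/100/200 trials, three step sizes and 4,000 replicates.

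- Go accuracy, all trials: power 31-71%.
- Go accuracy, 20 dropped: 4-17%.
- Go accuracy, calibrated start: about 5%.
- Fixed-difficulty accuracy: about 44-60%.
- Staircase level: 75-93%.

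With no extra shift, rejection was about 5-6% or less for both go accuracy and staircase level.

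**7. Pooling.** If go trials are a share g of all trials and go accuracy is equalised, a 10-point stop-trial difference becomes (1 − g) × 10: 7.5 points at g = 0.25, 5 at 0.5 and 2.5 at 0.75. The share is not stated.

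**The case against.** The strongest reply is that only go trials are titrated. If accuracy was meant as stop-trial accuracy there is no conflict, and if it was meant as overall accuracy the conflict is partial. That is right, but the text does not say so, and following it as written brings the titrated trials in.

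The second reply concerns size. With all trials scored, power for staircased go accuracy (31-71%) brackets that for ordinary fixed-difficulty accuracy (about 44-60%), and at the smallest step it exceeds it (68-71% against 46-58%). Compression in points overstates the loss because the spread shrinks too. This stands: in that scenario low power cannot be put down to titration alone. The collapse needs dropped early trials or calibrated starts, and the plan states neither. It rules out neither as well, so the same true effect could be found or missed on an unstated detail.

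Third, the simulation treats threat as a pure shift on the staircase's own scale, which favours the staircase level. A shift in willingness to lift is plausible when errors on any trial can bring a shock. This also stands, and it limits how the level should be used.

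Finally, the reach is modest. Section 9 lists fMRI and MEG as primary outcomes, task accuracy is in neither outcome list, and reaction time remains as a second behavioural measure. Equalising performance may well suit the imaging contrast; nothing here argues against titration itself.

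**Conclusion.** The point holds. The plan equalises go accuracy across conditions and then uses an accuracy difference, not limited to untitrated trials, as a measure of avoidance. The inconsistency follows from the text alone. Its size does not: depending on assumed settings, the go-accuracy difference keeps anything from almost nothing to somewhat over half of a 12-point effect (6.7/12 = 56%).

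A null go-accuracy result therefore cannot be interpreted without the staircase settings. The behavioural part of hypothesis F is affected, both the PTSD comparison and the brain-behaviour association. Stop-trial accuracy is not stated to be titrated, nor is reaction time, although reaction time would be affected if the titrated parameter is a response deadline. The neural contrasts and the sample size of 34 are untouched. This should be fixed, but it does not threaten the primary outcomes.

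**What to change.** In the outcome paragraph of the Active Avoidance section:

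1. Name the trial type wherever accuracy is used. Keep go accuracy only as a check that titration worked.
2. Add the threat-minus-safe difference in staircase level as a named measure for the PTSD comparison and the brain-behaviour correlations. State the titrated parameter, starting level, step rule, number of go trials per condition and any early trials left unscored.
3. Report stop-trial errors by condition, not pooled with go trials.
4. Read reaction time alongside the staircase level. A level driven by go trials alone mixes sensitivity with willingness to lift, so interpret it with stop-trial errors and do not make it the sole primary behavioural measure.

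The cost is protocol wording and an instruction to save the staircase level on each trial. The task generates that value, but the documents do not say it is kept. No extra participants, sessions or shocks are needed. If the titrated parameter is a response deadline, the level and reaction time overlap and are not independent evidence.
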